## 3.2. Secondary Endpoints

An e-Diary on a handheld device is to be provided to each participant at baseline, which is to be used until the end of study. The participants are required to enter any occurrence of bleeding episodes (including date, time, location, and etiology) and any exogenous FVIII replacement (including date, time, reason, and dose) required to treat the bleeds in the e-Diary throughout follow-up regardless of whether or not the participant has initiated or resumed prophylactic therapy. If a participant has to initiate or resume FVIII prophylaxis

treatment, prophylaxis FVIII infusion data will not have to be reported on the e-Diary after Month 24 but the prescribed FVIII replacement regimen will be recorded in the eCRF by the sites and used to derive infusion data. On-demand and preventative infusions will continue to be required to be reported on the e-Diary throughout follow-up.

The protocol recommends prophylaxis FVIII treatment for up to approximately 2 weeks post PF-07055480 infusion (and may be used longer than 2 weeks, per investigator discretion), to provide protection against bleeding while allowing sufficient time for PF-07055480 to start FVIII expression. Participants are then switched to on-demand regimen. The first 3 weeks following treatment with PF-07055480 will not be considered in the analysis of annualized infusion rate (AIR) and annualized bleeding rate (ABR), to exclude contributions from prior routine prophylaxis, which could have been continued during this period.

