### 3.2.1. Annualized Infusion Rate

The FVIII Administration electronic case report form (eCRF) and e-Diary will be used to collect each participant's pre-IP infusion FVIII medication details (including reason for infusion) beginning 30 days prior to the Screening visit through the Baseline visit (eCRF), and from Baseline to just before the IP infusion (e-Diary).

For pre-IP infusion, the AIR will be calculated in two ways:

- $[(\text{number of FVIII replacement infusions for reasons other than prophylaxis prior to IP infusion}) / (\text{[date of IP infusion} - \text{date of screening}] + 30)] * 365.25$ .
- $[(\text{number of FVIII replacement infusions for any reason prior to IP infusion}) / (\text{[date of IP infusion} - \text{date of screening}] + 30)] * 365.25$ .

Reasons for FVIII replacement therapy other than prophylaxis will include selective prevention of bleeding, prophylaxis for invasive procedures, and bleeding. In case a frequency other than "Once" is selected, the number of FVIII infusions to be added to the numerator of the above will be calculated based on the frequency of FVIII infusions and duration of treatment. A frequency of once per day will be used for frequencies listed as burst, taper, and titrate.

For post-IP infusion, the annualized infusion rate will be assessed as  $[\text{number of FVIII replacement infusions starting at 3 weeks (ie, Day 22 post-IP infusion)} / \text{(number of days in the observation period for the participant in years)}]$ . If the participant discontinued from study before the end of the prespecified time period, the last date in the observation period will be the date of study discontinuation. For all participants, post-IP infusions (and days for the denominator) will be counted beginning on Day 22, and will stop counting when (the first of) any of the following things happen:

1. The subject completes or discontinues (this day will be counted if data were collected).
2. Data cut or freeze date (this day will be counted if data were collected).

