The number of days in the observation period will be calculated as (date of data cut [or conclusion date] – [date of IP infusion + 21 days] + 1), which will then be annualized within the AIR formula. All infusions during the observation time period for any purpose (to treat bleeding, for preventive purpose, perioperative, or if FVIII prophylaxis regimen is initiated or resumed) will be included in the calculation of AIR. If no FVIII replacement infusions are reported during an observation period, AIR will be reported as zero.

A within-participant absolute difference, as well as percent reduction from pre-IP infusion AIR, will be calculated and summarized for the pre-study infusion calculation method that includes FVIII replacement therapy for any reason.

The five yearly windows defined in [Section 5.2](#) will be used for this AIR analysis. An additional observation period is defined for the entire length of follow-up, >week 3 through Year 5.

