### 3.2.2. Annualized Bleeding Rate

The number of bleeding episodes (BEs) during 12 months prior to the Screening visit will be collected in the Hemophilia History eCRF directly and will be used as the pre-screening rate. This form does not distinguish between treated or untreated bleeding episodes, only “total” pre-screening rate will be available.

The post-IP treated ABR will be calculated as:

$$[(\text{number of BEs requiring FVIII treatment recorded for the participant starting 3 weeks after IP infusion}) / (\text{number of days in observation period for the participant})] * 365.25.$$

If a FVIII prophylaxis regimen is initiated or resumed for a participant, then the time period (beginning with the first day of prophylaxis initiation or resumption) will be excluded from the treated ABR. The bleeding events after prophylaxis initiation or resumption will be excluded and the time period while on prophylaxis regimen will be deducted from the observation period, as well.

For all participants, treated bleeds (and days for the denominator) will be counted beginning on Day 22, and will stop counting when (the first of) any of the following happen:

1. The subject initiates or resumes routine prophylaxis (first day of resumption will not be counted);
2. The subject completes or discontinues (this day will be counted if data were collected);
3. Data cut or freeze date (this day will be counted if data were collected).

The number of days in the observation period will be calculated as (date of day before start of prophylactic dosing [or date of data cut or conclusion date] – [date of IP infusion + 21 days] + 1) which will then be annualized within the treated ABR formula. If no treated

bleeding episodes are reported during an observation period, treated ABR will be reported as zero.

During the post-IP period, multiple concurrent BEs (eg, two or more BEs that occur on the same date and time but in different sites in a participant) will be recorded as one bleed for overall treated ABR, but as separate BEs for that participant for treated ABR by location type (one episode for each unique location type, if they are different). Both spontaneous and traumatic treated bleeds will be counted towards the derivation of overall treated bleeding rate. BEs associated with a surgical procedure (perioperative and/or during the surgical rehabilitation period) will not be included in the treated ABR calculation.

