##### 5.2.1.1. Yearly Windowing

The following windowing option may be used when each yearly observation period used for analysis will be 365 days. Any dates beyond 1460 days will also be included with Year 5 for analysis. Post-infusion AIR and ABR yearly windowing begins with 3 weeks after the IP infusion where day is calculated relative to the IP infusion date. Post-infusion AE yearly windowing begins on the IP infusion date.

Window name	Derivation
Year 1	Day 22 $\leq$ Year 1 $\leq$ Day 365
Year 2	Day 365 < Year 2 $\leq$ Day 730
Year 3	Day 730 < Year 3 $\leq$ Day 1095
Year 4	Day 1095 < Year 4 $\leq$ Day 1460
Year 5	Day 1460 < Year 5

Further details of windowing will be described separately for each endpoint in [Section 2.1](#), as applicable.

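### Read literally, the SAP's zero rule reports treated ABR as 0 for a yearly window with no eligible days, such as any year wholly after a return to prophylaxis

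*SAP*

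**What the plan says.** **Treated ABR (SAP 3.2.2).** Counting starts on Day 22 and ends at the first of several events. One of these is "The subject initiates or resumes routine prophylaxis (first day of resumption will not be counted"). Later bleeds are excluded, and "the time period while on prophylaxis regimen will be deducted from the observation period, as well". The zero rule follows: if no treated "bleeding episodes are reported during an observation period, treated ABR will be reported as zero".

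**AIR (SAP 3.2.1).** The parallel rule is "If no FVIII replacement infusions are reported during an observation period, AIR will be reported as zero". The stopping events are completion or discontinuation and the data cut or freeze. Prophylaxis is not one of them. After early withdrawal, "the last date in the observation period will be the date of study discontinuation".

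**Windows (SAP 5.2.1.1).** The SAP applies the word period to each year: "each yearly observation period used for analysis will be 365 days". SAP 3.2.1 and 3.2.2 both use the five yearly windows and add a further observation period for the whole of follow-up.

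**Who is summarised (SAP 6.2.1 and 6.2.2).** Both rates are summarised by these intervals in the Safety population. No condition is set on eligible time within a window.

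**The concern.** A zero rule is sensible for a participant who was observed and did not bleed. It is not sensible for one who contributed no time at risk. The rule as written does not separate the two cases.

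The direction matters. A return to prophylaxis plausibly signals that expression was no longer sufficient. If the years that follow are scored 0, that participant enters the later-year treated ABR tables with the best attainable result, and the mean falls further as more participants go back on prophylaxis. Protocol 9.4.3 gives durability of effect as one reason for following participants through Years 2 to 5, so these are the tables in which the artefact would appear.

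**Working it through.** The plan states no figure to reproduce. The check applies the SAP's own counting rules.

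**Inputs from the SAP**
- Day 1 is the infusion date (Section 5), so the infusion date plus 21 days is Day 22.
- Windows (5.2.1.1): Year 1 is Days 22–365, Year 2 is 366–730, Year 3 is 731–1095, Year 4 is 1096–1460, and Year 5 is after Day 1460.
- Rate = events / eligible days × 365.25. The day formulas in 3.2.1 and 3.2.2 cover the whole of follow-up and are not restated by year. Eligible days in a window are taken here as the overlap of the window with the span from Day 22 to the last counted day.

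**Assumptions, not from the documents:** prophylaxis resumed on Day 600; separately, withdrawal on Day 800; last visit on Day 1826.

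**1. Eligible days by year**

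| Case | Y1 | Y2 | Y3 | Y4 | Y5 |
|---|---|---|---|---|---|
| Treated ABR, prophylaxis from Day 600 | 344 | 234 | 0 | 0 | 0 |
| AIR, same participant | 344 | 365 | 365 | 365 | 366 |
| AIR, withdrawal on Day 800 | 344 | 365 | 70 | 0 | 0 |

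For example, Year 1 is 365 − 22 + 1 = 344, treated ABR Year 2 is 599 − 366 + 1 = 234, and AIR Year 3 after withdrawal is 800 − 731 + 1 = 70. For the first participant, treated ABR in Years 3–5 is 0/0, and the only sentence that covers a period without events gives 0. The whole-follow-up rate remains defined, on 599 − 22 + 1 = 578 days.

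**2. AIR after a return to prophylaxis.** Infusions given "perioperative, or if FVIII prophylaxis regimen is initiated or resumed) will be included in the calculation of AIR". After Month 24 the "prescribed FVIII replacement regimen will be recorded in the eCRF by the sites and used to derive infusion data". At an assumed 2 to 3 infusions a week, AIR is 2 × 365.25/7 = 104 to 3 × 365.25/7 = 157 a year, so it is not 0.

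**3. Effect on a yearly mean.** If k of n participants have empty windows and each is scored 0, the mean over the n − k observed participants is multiplied by (n − k)/n.

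| n | k = 1 | k = 2 | k = 3 |
|---|---|---|---|
| 5 | 0.80 | 0.60 | 0.40 |
| 10 | 0.90 | 0.80 | 0.70 |
| 20 | 0.95 | 0.90 | 0.85 |

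Two illustrations with assumed treated ABRs:
- Values 2, 3, 4 and two empty windows: with the empty windows omitted, mean 9/3 = 3.0 and median 3; scored 0, mean 9/5 = 1.8 and median 2.
- Values 0, 0, 1, 4 and one empty window: omitted, mean 5/4 = 1.25 and median 0.5; scored 0, mean 5/5 = 1.00 and median 0.

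**4. Non-positive days.** If prophylaxis restarts on Day 18, the 3.2.2 formula gives 17 − 22 + 1 = −4 days, and the zero rule would still give 0.

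**5. Very short windows.** With Poisson bleeding at an assumed true rate of 5 a year, the chance of no bleed is exp(−5 × 7/365.25) = 0.91 in 7 days and exp(−5 × 30/365.25) = 0.66 in 30 days. One bleed in 7 days annualises to 365.25/7 = 52.2.

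**The case against.** The best reply is that the SAP does not direct anyone to score an empty window as 0. It makes the observation period specific to the participant: the period ends at discontinuation for AIR, and prophylaxis time is deducted from it for treated ABR. A year with nothing left may therefore hold no observation period, so the zero rule is never triggered. SAP 5.3 sets a general default of no imputation, and SAP 6.5.2 lists the years that a participant entered. The yearly windowing in 5.2.1.1 is itself worded as an option.

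This reading is tenable, but it is not secured. The default in 5.3 exempts rules given in Section 3, which is where the zero rules are. The 6.5.2 provision governs a listing, and a participant back on prophylaxis is still in the study and has entered the later years. SAP 6.1.1 defines a yearly denominator for adverse events, and ABR and AIR have no counterpart. Two programmers could produce different tables from the same text.

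Other parts of the reply stand:
- A reader might infer that AIR also falls to 0 after a return to prophylaxis. It does not; it would be high, so that companion endpoint would show the loss of effect.
- The cut-off and zero rule in 3.2.2 are written for treated ABR. The SAP does not say whether they extend to total ABR, which is the rate compared with pre-screening.
- SAP 6.2.2 already lists ABR after initiation or resumption of prophylaxis, and 6.5.2 lists each participant's duration in each year. With about 20 participants, a careful reader could find those affected. The listings do not correct the summary tables.
- The negative-day case is rare. SAP 3.2 allows prior prophylaxis to run beyond two weeks, and continuing it is not obviously the same as initiating or resuming it.

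**Conclusion.** The point holds for treated ABR in years wholly after prophylaxis is initiated or resumed, and for treated ABR and AIR in years wholly after withdrawal or the data cut. In those windows the literal rule turns an undefined rate into 0, and no other provision clearly prevents it.

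The size depends on how many windows are empty, which the documents do not give. The factor (n−k)/n is exact for the mean; the cohort sizes, counts of empty windows and bleeding rates used above are assumed. In a small dose cohort even one or two empty windows matter.

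Two stronger conclusions are not supported. The SAP does not expressly state that empty windows score 0. Nor is the mean over participants still off prophylaxis an unbiased measure of durability: those participants are a selected group, so omitting empty windows removes the artefact but not the selection. The endpoint is secondary and SAP 5.1 plans no formal inference, so no error rate or power is affected. The correction should still be made, because the distortion favours the product and is cheap to remove.

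**What to change.** In SAP 3.2.1 and 3.2.2, replace the zero sentence with a rule to this effect: the rate is set to zero only when no event is reported and the participant has at least one eligible day in the window; it is missing when eligible days are zero or the day formula is negative. Define eligible days as the overlap of the yearly window with the participant's counted period.

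State in 3.2.2 whether the prophylaxis cut-off and the zero rule also apply to total ABR.

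Print the number of participants contributing and the total eligible days beside each yearly ABR and AIR. The non-missing n in SAP 5.2.3 will be right once empty windows are missing, so eligible days is the only new quantity. It is needed because a one-day minimum still admits unstable short windows, and because readers should see how selected the group remaining off prophylaxis has become.

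The cost is one sentence in each of two sections, one clarification on total ABR, and one or two table columns. No new data are needed.

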5.1. Inclusion Criteria

Participants are eligible to be included in the study only if all of the following criteria apply:

1. Signed informed consent.
2. Male ≥ 18 years of age able to understand the informed consent.
3. Severe hemophilia A (with past evidence of circulating FVIII activity of <1% normal).
4. Treated or exposed to FVIII concentrates or cryoprecipitate for at least 150 exposure days.
5. ≥ 12 bleeding episodes if receiving on-demand therapy over the preceding 12 months.

6. Sexually active participants must agree to use double barrier contraceptive (one of them being a condom) or abstinence, and all participants must refrain from donating their sperm until at least 3 consecutive semen samples after SB-525 (PF-07055480) treatment are negative for AAV2/6 and for a minimum of 90 days after SB-525 (PF-07055480) administration.

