6.5. Concomitant Therapy

All concomitant medications and therapy taken through Month 36 must be captured in the CRF. After Month 36, only concomitant medications and therapy associated with SAEs, AEs related to the study drug, or to AEs with an unknown cause will be reported through Month 60 or the ETV, if applicable. See Section [8.3.1](#) for AE reporting requirements.

The investigator will record all concomitant medications including those given in treatment of AEs on the concomitant medication page in the participant's CRF. Any medication taken by the participant from 30 days prior to screening throughout the course of the study, including over-the-counter medicinal products, dietary supplements, and herbal medications, should be recorded on this form. A short course of prednisone may be instituted either as prophylaxis or post AAV exposure if an immune reaction to the AAV capsid develops (Section [10.7](#)). Any treatment with prednisone and pre-treatment with acetaminophen and diphenhydramine hydrochloride should be recorded on the concomitant medications page.

Participants enrolled in this study who previously received prophylactic FVIII replacement regimens will be required to switch to on-demand therapy approximately 2 weeks after infusion with SB-525 (PF-07055480), pending data shows it is safe to do so. The use and timing of FVIII replacement will be monitored closely in this study and will influence the timing of PD assessments for FVIII activity. There is no washout period per se, but all participants will be switched to an on-demand regimen approximately 2 weeks after infusion and subsequently modulate their FVIII replacement use according to their needs. All participants are to carefully record the date and time of each FVIII administration in an e-Diary, so that the elapsed time between their last FVIII administration and each FVIII level collection can be collected. For participants using short half-life replacement products, the resulting FVIII levels are valid only if elapsed time is more than 48 hours. For participants using extended half-life FVIII replacement products, this time is extended to 72 hours. Of note, 48 and 72 hours are reference values, these times can be modified depending on the participant profile (slow versus fast metabolizers) and the prescribing information of each product. The investigator may recommend a different time for his/her study participant after discussion with the medical monitor.

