Because only total ABR is available for pre-screening, overall total post-IP ABR will also be calculated, including BEs with and without FVIII treatment. A within-participant absolute difference, as well as percent reduction from pre-screening ABR, will be calculated for total ABR and summarized.

Treated and total ABRs will also be derived by location type (joint, target joint, soft tissue/muscle/other), by cause (spontaneous BE and traumatic BE), and by BE severity (mild, moderate, severe).

The five yearly windows defined in [Section 5.2](#) will be used for treated and total ABR analysis. An additional observation period is defined for the entire length of follow-up, >week 3 through Year 5.

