### 6.2.2. Annualized Bleeding Rate

Both pre-screening and post-IP infusion total ABRs will be summarized together with the difference and percent reduction, along with the summary of post-IP infusion treated ABR, for the Safety population by dose level. The number and percentage of participants with no bleeds post-IP infusion will also be summarized by dose level. All participants, regardless of prior prophylaxis treatment status, will be included. Post-IP infusion treated and total ABR will be summarized by the time intervals as specified in [Section 3.2.2](#).

Separate summaries of treated and total post-IP infusion ABR by location type (joint, target joint, soft tissue/muscle/other), by cause (spontaneous and traumatic BEs), and by BE severity will be created for the Safety population stratifying by dose level.

Additional analyses may be performed using an Evaluable population, if appropriate.

Listings of BEs recorded during the study and the annualized rates will be created. The listing will additionally include treated and total post-initiation or post-resumption of prophylaxis ABR for the participants who initiated or resumed a FVIII prophylaxis treatment during the post-infusion period.

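### The percent reduction in total ABR has no value for a zero-bleed history and pools two different before-and-after contrasts; a ratio of mean ABRs and one table by prior regimen would address both

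*SAP*

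**What the plan says.** The count of bleeds in the 12 months before Screening "will be collected in the Hemophilia History eCRF directly and will be used as the pre-screening rate" (SAP 3.2.2). The same section then plans a within-participant absolute difference and, in the same sentence, says that the "percent reduction from pre-screening ABR, will be calculated for total ABR and summarized". SAP 6.2.2 puts these results in one summary, by dose level in the Safety population: "Both pre-screening and post-IP infusion total ABRs will be summarized together with the difference and percent reduction". It adds: "All participants, regardless of prior prophylaxis treatment status, will be included".

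Inclusion criterion 5 in Protocol 5.1 asks for "≥ 12 bleeding episodes if receiving on-demand therapy over the preceding 12 months". No minimum is given for participants on prophylaxis, and they are clearly eligible. Protocol 6.5 says: "Participants enrolled in this study who previously received prophylactic FVIII replacement regimens will be required to switch to on-demand therapy", at about two weeks after infusion.

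SAP 3.2.2 sets the treated ABR to zero when no treated bleeds occur after infusion, but has no rule for a pre-screening count of zero. SAP 5.3 generally does not impute. SAP 5.2.3 summarizes continuous variables on non-missing values, with n, mean, SD, median, quartiles and extremes. SAP 6.4 plans no subset analyses.

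**The concern.** Two separate problems affect the percent-reduction column.

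- **Undefined values.** A participant with no bleeds in the history year cannot improve, so the percentage is missing only for people who stayed the same or got worse. The loss therefore runs in one direction. A history of one or two bleeds does give a value, but a few later bleeds turn it into a large negative number that dominates a mean in a small cohort.
- **Two contrasts in one figure.** For a prior-prophylaxis participant the change compares bleeding on prophylaxis with bleeding after stopping it. For an on-demand participant it compares two periods without prophylaxis, starting from a year selected to have at least 12 bleeds. A pooled percentage answers neither question, and it shifts with the proportion of each type enrolled.

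ABR change serves the secondary objective on clinical impact. About 20 participants are planned, and SAP 6.5.3 lists four dose cohorts, so each row is small.

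**Working it through.** **Plan's own figure.** There is none to reproduce. The documents give no expected ABR, effect size or regimen mix, and the sample size is not based on a calculation. All bleed rates below are assumptions.

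**1. Where the percentage fails.** Individual reduction = 100 × (1 − post/pre). At pre = 0 it has no value. Criterion 5 rules out zero for on-demand participants, so only prior-prophylaxis participants are affected.

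**2. How likely a zero history is.** For an assumed mean of m bleeds per year on prophylaxis, P(0) = exp(−m) under a Poisson model, or (1 + m/k)^(−k) under a negative binomial, here with k = 1. P(at least one zero among five) = 1 − (1 − P(0))^5.

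| m | P(0), Poisson | At least 1 of 5 | P(0), k = 1 | At least 1 of 5 |
|---|---|---|---|---|
| 1 | 37% | 90% | 50% | 97% |
| 2 | 14% | 52% | 33% | 87% |
| 3 | 5% | 23% | 25% | 76% |
| 5 | 0.7% | 3% | 17% | 60% |

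**3. A constructed cohort of five.** Pre = 0, 1, 2 (prior prophylaxis) and 15, 30 (on-demand); post = 1, 2, 1, 1, 1.

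- Individual reductions: undefined, −100%, 50%, 93.3%, 96.7%. On n = 4 the mean is 140/4 = 35.0% and the median is 71.7%.
- Ratio of means, all five: 100 × (1 − 1.2/9.6) = 87.5%.
- By prior regimen: prophylaxis 100 × (1 − 1.33/1.0) = −33.3%; on-demand 100 × (1 − 1.0/22.5) = 95.6%.

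The ratio of means restores the missing participant. Only the split shows that the two groups moved in opposite directions.

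**4. Case mix.** Let everyone have a post ABR of 1, with pre ABR 2 (prophylaxis) or 20 (on-demand).

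| On-demand share | Mean individual reduction | Ratio of means |
|---|---|---|
| 0% | 50% | 50% |
| 25% | 61% | 85% |
| 50% | 73% | 91% |
| 75% | 84% | 94% |
| 100% | 95% | 95% |

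Both measures move with the mix, so a change of formula does not remove this part.

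**5. Which group formula.** Post-infusion time varies between participants. Suppose A bleeds 20 times a year before and after but is observed for 0.25 years (5 bleeds), and B bleeds twice a year before and after over 5 years (10 bleeds). Nobody has changed.

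- Total events over total years: 100 × (1 − (15/5.25)/(22/2)) = 74%, a false reduction.
- Ratio of mean ABRs: 100 × (1 − 11/11) = 0%, which is correct.

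**6. Regression to the mean from the 12-bleed floor.** In simulated on-demand participants with no treatment effect, Poisson counts and either a common rate or gamma-distributed rates (shape 2 or 4), the mean ABR falls by about 6% to 18% if the true mean is 12, 4% to 7% if it is 15, and 0% to 3% if it is 20 to 30. This is the smallest of the effects.

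**The case against.** The strongest reply is that the percentage never stands alone. SAP 6.2.2 shows pre and post total ABR and the absolute difference beside it, and all three are defined for a zero history. SAP 5.2.3 adds n, the median and the quartiles. With histories 0, 0, 1, 12, 20 and post-infusion rates 1, 1, 3, 1, 1, the individual reductions are −200%, 91.7% and 95%: the mean is −4%, but the median is 91.7%, and n = 3 reveals the two missing values. Individual rates are listed as well. All of this stands. A reader might infer that the whole bleeding summary is biased, or that one participant can reverse it. The documents do not support that: the fault lies in one column, and the instability is in the mean.

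A reader might also infer that pooling is a mistake in the plan. It is a stated choice in a descriptive study without hypotheses, and type of FVIII treatment is summarized at baseline (SAP 6.5.5), so the split could be partly rebuilt. However, no planned table shows ABR change by prior regimen.

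Finally, within-participant might qualify only the absolute difference in SAP 3.2.2. A percentage calculated and summarized beside it is most naturally individual too. If a group figure was meant, the undefined-value problem largely disappears, the wording needs clarifying, and the pooling point remains.

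**Conclusion.** The concern holds as a cheap improvement. The percent-reduction column cannot include a participant with a zero history, eligibility permits such participants, and those excluded could not have shown a benefit. The pooled percentage also depends on the regimen mix.

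The size is unknown. The documents do not show that any zero-history participant was enrolled, and the 50% to 95% range and the probabilities above rest on assumed rates. The description of the prophylaxis contrast assumes that these participants were on prophylaxis during the history year. It also assumes that time after prophylaxis is resumed is left out, which SAP 3.2.2 states only for treated ABR.

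A reader might take pooled events over pooled years as the obvious replacement. It is unsafe here, because SAP 3.2.2 lets post-infusion time differ between participants, and step 5 shows a 74% reduction arising from no change.

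**What to change.** In SAP 3.2.2 and 6.2.2:

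- Keep the within-participant absolute difference as the main measure of change.
- Report the group percent reduction as 100 × (1 − mean post-infusion total ABR / mean pre-screening total ABR), by dose level and overall, over all participants with a post-infusion ABR and including zero histories. Take both means over the same participants in each observation window. If every history in a row is zero, show the difference only.
- Do not use total events over total years.
- If individual percentages are kept, give the number not calculable and rely on the median.
- Add one overall table, not one per cohort, of pre, post and change in total ABR by prior regimen (on-demand versus prophylaxis).

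The cost is SAP wording and one table with small rows, from data already collected. The ratio of means has limits: it gives more weight to participants with high histories, and a short observation period can produce an extreme post ABR (one bleed in 0.25 years counts as 4 per year). That is why the absolute difference should lead.
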